Participants will be assigned to a study cohort based on the treatment that was received during the recruitment period. All participants receiving Roctavian during the recruitment period will be assigned to the Roctavian Cohort. Participants receiving SoC hemostatic prophylaxis treatment only during the recruitment period will be assigned to the SoC Cohort. Index date will be defined as the date of Roctavian administration for PwSHA treated with Roctavian (Roctavian Cohort) and the date of consent for PwSHA treated with SoC products (SoC Cohort). Participants will be followed for 3 years after index date (follow-up period) based on data extracted from the DHR. If a participant consents to the AbD while on SoC and subsequently receives Roctavian during the recruitment period, inclusion/exclusion will be reassessed at the time of Roctavian administration. For these participants, baseline assessments, including patient reported outcome measures, will also be re-assessed at the time of Roctavian administration. If a participant in the SoC Cohort subsequently receives Roctavian during follow-up after the recruitment period, their data will be censored for analysis (censoring discussed further in Section 10.3). Study participants will be followed consistent with the Study Elements of Interest (see Section 7.1) from index through the follow-up period. The study aims to enroll at least 70 PwSHA into the Roctavian Cohort and at least 330 PwSHA into the SoC Cohort. The study is anticipated to complete approximately 6 months prior to the final report required to be submitted to G-BA. Figure 2 illustrates the overall study conduct. The study completion date is based on allowing time to analyze data and submit a final report on the AbD defined by the G-BA resolution. Changes to the AbD defined deadlines for the final report would result in changes to the study completion timeframe, as well as the recruitment window described above.

Figure 1: Study Schema

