8.2. Lost to Follow-Up

It is not anticipated that participants will be lost to follow-up due to the routine clinical management of PwSHA, as well as data being collected consistent with ongoing disease management practices. However, a participant may be considered lost to follow-up if he repeatedly fails to attend visits at the study site or does not respond to attempts at contact made by the study site. A participant will be deemed lost to follow-up at the discretion of the participant's treating physician, as participants are expected to be seen consistent with routine clinical management. As PwSHA are expected to be seen at an HTC at least annually

(and likely every 6 months), a participant may be considered lost to follow-up if he has not been seen, or no data has been reported into the DHR (whichever is later) for 18 months. Before a participant is deemed lost to follow-up, the treating physician or designee should make every effort to regain contact with the participant.

For the purposes of analyses, a participant's follow-up will be censored at the end date of the most recent data entry period into the DHR. At the time of final data cut, any participant without data entered into the DHR over the full follow-up period of this AbD (index date + 3 years) will be considered lost to follow-up and similarly censored. In reporting participants lost to follow-up, participants deemed lost to follow-up at the discretion of the investigator will be reported separate from those considered lost to follow-up at the time of the final data cut.

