Time between Roctavian administration (index date) and resumption of hemostatic prophylaxis (defined in [Table 7](#)) will be described for the Roctavian Cohort only. The proportion who return to prophylaxis and time to resumption will be described among those in the cohort who ended prophylaxis post Roctavian administration. Summary statistics will

be utilized to describe time to resumption including mean (SD), median (inter quartile range), minimum and maximum. Treatment utilization patterns in the 3 and 6 months after the resumption of prophylaxis will be described regarding the number of infusions/injections by prophylaxis treatment class, total FVIII dose for participants returning to prophylaxis with FVIII, and frequency of infusions/injections will be described.

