On-demand hemostatic treatments	Yes (calculated)	
 Occasion Preparation/medicinal product Weight Consumption/delivery Treatment date Start of reporting period 	
 Amount of on-demand FVIII utilized per participant over time (IU or mg), as well as per participant per kg over time (IU/kg) for FVIII products and mg/kg for emicizumab for a bleeding event (occasion = "suspected bleeding", "spontaneous bleeding", "traumatic bleeding/bleeding", or "intensified on-demand treatment (=short-term prophylaxis)") Amount of on-demand FVIII utilized per participant over time (IU or mg), as well as per participant per kg over time (IU/kg) for FVIII products and mg/kg for emicizumab for short-term prophylaxis (occasion = "intensified on-demand treatment (=short-term prophylaxis)") 	
 ≥1 year ≥2 years ≥3 years All available follow-up

Variable	Captured in DHR	DHR data field name(s)	Operational definition and calculation of outcome measures	Timepoints for data collection
		
 End of reporting period 	
 Each participant's average weight over the reporting period will be used when calculating IU/kg 	
FVIII Infusion/injection rate	Yes (calculated)	
 Preparation/ medicinal product Frequency Start of reporting period End of reporting period 	
 Number of infusions/injections from the index date through the follow-up period Derived based on the therapy usage and frequency of use during individual usage periods recorded in the DHR for any reason and summarized as AIR 	
 ≥1 year ≥2 years ≥3 years All available follow-up
Time to resumption of prophylactic treatment	Yes	
 Did the patient have to return for prophylaxis? Date of return to prophylaxis Date of gene therapy 	
 Roctavian Cohort only Derived based on the recording of whether the patient had to return for prophylaxis and if yes, the time (days) between the date of gene therapy and date of return to prophylaxis 	All available follow-up
Clinical Outcome Assessments				

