7.9.4.6. Time to Resumption of Prophylactic Treatment

Population	Measurement Period	Analysis Notes
Roctavian Cohort only	All available follow-up data	Definition utilized in this study is relevant to the fields that the DHR collects and will be aligned as best as possible to other definitions utilized external to this study

For participants in the Roctavian Cohort, time to resumption of prophylactic treatment will be measured for participants who received SoC prophylaxis after Roctavian administration during the follow-up period. Treatment utilization patterns in the 3 and 6 months after the resumption of prophylaxis will be described regarding the number of infusions/injections by prophylaxis treatment class, total FVIII dose for participants returning to prophylaxis with FVIII, and frequency of infusions/injections. Summary statistics will be utilized to describe time to resumption including mean, SD, median, IQR, minimum, and maximum.

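### Time to resumption of prophylaxis is summarised among resumers only and without censoring, so its mean and median hardly respond to durability once the true median reaches the 3-year follow-up

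*Protocol*

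**What the plan says.** Protocol section 10.3.7.6 defines the quantity as "Time between Roctavian administration (index date) and resumption of hemostatic prophylaxis" and says summary statistics will "be utilized to describe time to resumption including mean (SD), median (inter quartile range), minimum and maximum". On the population it says: "The proportion who return to prophylaxis and time to resumption will be described among those in the cohort who ended prophylaxis post Roctavian administration".

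The SAP text bound with the protocol follows the same line:

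- SAP Table 5 (section 7.4.3) derives the variable from the registry's return-to-prophylaxis field: "if yes, the time (days) between the date of gene therapy and date of return to prophylaxis". A participant who has not returned therefore has no value.
- SAP section 7.9.4.6 words the population differently: "time to resumption of prophylactic treatment will be measured for participants who received SoC prophylaxis after Roctavian administration during the follow-up period". It lists the same summary statistics.
- Table shell 18 in SAP Annex 12.1 has the number and percentage who resumed, then mean, SD, median, quartiles, minimum and maximum in days. It has no row for an estimate that uses censored participants.

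Follow-up has a fixed end. Protocol section 5.1 says: "Participants will be followed for 3 years after index date (follow-up period) based on data extracted from the DHR". Section 8.2 gives a general rule that a participant's "follow-up will be censored at the end date of the most recent data entry period into the DHR", but section 10.3.7.6 does not take it up.

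**The concern.** This is a time-to-event objective analysed as if every participant had an observed time. Those who have not resumed by 3 years, or who die, withdraw or are lost before resuming, drop out of the mean and median. What remains describes how early the resumers resumed, given that they did so within the window. It does not describe how long participants stay off prophylaxis.

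For a one-time gene therapy under benefit assessment, a reported mean of about 1.4 years could easily be read as the duration of effect. That would understate a durable product and would barely separate it from a weaker one. The number also depends on how long participants have been followed, so the interim and final reports would differ even if nothing about the therapy did.

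**Working it through.** The documents give no figure for time to resumption, so there is nothing of the plan's own to reproduce.

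**Inputs.** From the documents: 3 years of follow-up (protocol 5.1), 70 Roctavian participants (protocol 5.1), and interim reports at 18, 36 and 54 months using data from about 4 to 6 months earlier (protocol 10.4). Assumed, because the documents do not give it: the distribution of time to resumption. It is taken as Weibull with shape k from 0.7 to 3 (k = 1 is a constant hazard) and true median m from 1 to 20 years.

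**Formulas.** F(t) = 1 − 2^(−(t/m)^k). The planned mean estimates E[T | T ≤ 3] = ∫₀³ t f(t) dt / F(3). For a constant hazard h = ln 2 / m this is 1/h − 3e^(−3h)/(1 − e^(−3h)). For m = 3: h = 0.231, 1/h = 4.33, e^(−3h) = 0.5, so the mean is 4.33 − 3 × 0.5/0.5 = 1.33 years. An analysis that used censoring would estimate F(3), or the 3-year restricted mean (1 − e^(−3h))/h.

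**Constant hazard, all followed for 3 years:**

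| True median (years) | Resumed by 3 years | Mean among resumers | Median among resumers | 3-year restricted mean |
|---|---|---|---|---|
| 1 | 88% | 1.01 | 0.83 | 1.26 |
| 2 | 65% | 1.24 | 1.13 | 1.87 |
| 3 | 50% | 1.33 | 1.25 | 2.16 |
| 5 | 34% | 1.40 | 1.35 | 2.45 |
| 10 | 19% | 1.45 | 1.42 | 2.71 |
| 20 | 10% | 1.47 | 1.46 | 2.85 |

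From a true median of 3 years to one of 20, the planned mean moves by 0.14 years while the proportion resumed falls from 50% to 10%. In simulation with 70 participants, 95% of the means lie in 1.05–1.62 for a true median of 3 years and in 0.96–1.95 for 10 years. The planned mean cannot tell the two apart.

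**Other hazard shapes, true medians 3 to 20 years.** Mean among resumers:

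- k = 0.7 (falling): 1.06–1.19
- k = 1.5: 1.64–1.79
- k = 2: 1.86–2.00
- k = 3: 2.14–2.25

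When few resume, F(t) is nearly proportional to t^k and the mean tends to 3k/(k + 1): 1.24, 1.50, 1.80, 2.00 and 2.25 for k = 0.7, 1, 1.5, 2 and 3. Only shape and follow-up length enter this limit; the true median does not. Starting the risk of resumption 0.2 years after infusion (assumed, for the period before prophylaxis ends) shifts the constant-hazard range to 1.44–1.58.

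**Shorter follow-up.** With 1.5 years for everyone and a constant hazard, the mean among resumers is 0.71–0.74 for true medians of 3 to 20 years. The 18-month report would have less still: 18 − 6 = 12 to 18 − 4 = 14 months at most. The crude proportion moves too. For a true median of 3 years it is 29% at 1.5 years and 50% at 3 years, so a proportion taken over mixed follow-up lies somewhere between and is hard to interpret.

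**The case against.** The strongest reply is that section 10.3.7.6 also plans the proportion who return, and that proportion does separate durable from short-lived effect, as the table shows. Recruitment is timed to give each participant 3 years, and section 8.2 does not expect loss to follow-up, so at the final analysis the crude proportion should be close to a 3-year cumulative incidence. This stands. The bias in the proportion matters mainly at the interims. But 10.3.7.6 gives the proportion no follow-up requirement, although sections 10.3.7.2, 10.3.7.3 and 10.3.7.5 restrict their proportions to participants with full follow-up.

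The objective is also descriptive, in one cohort, with no test. That limits the consequence. The general censoring rule in 8.2 and the mention in SAP section 7.7.1 that a survival package may be used are not linked to this endpoint, so they do not cure it.

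Three stronger readings are tempting and are not supported:

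- A reader might infer that the mean will be 1.3 to 1.5 years whatever the durability. That holds only for a roughly constant hazard and a true median of about 3 years or more. With true medians of 1 to 2 years the constant-hazard mean is 1.01 to 1.24, and other shapes give other levels.
- A reader might infer that the SAP 7.9.4.6 wording counts nearly everyone as resuming, because prophylaxis continues for some weeks after infusion. Protocol Table 7 and SAP Table 5 define the event as a recorded return to prophylaxis, so continued use after infusion is not an event. The two population statements still differ.
- A reader might infer that nothing else in the study speaks to durability. Bleeding rates by annual increment and hemostatic use in the second or third year also do.

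**Conclusion.** The point holds. The planned mean and median are conditional on resuming within follow-up and ignore censoring. Once the true median reaches the 3-year window they are nearly insensitive to durability: 1.33 to 1.47 years under a constant hazard, and between about 1.1 and 2.25 years across the shapes examined, with each shape almost flat in the true median. They also lengthen with follow-up, from 0.71–0.74 years at 1.5 years to 1.33–1.47 at 3 years under a constant hazard. The hazard shapes and true medians are assumptions; the truncation itself is fixed by the text. The primary comparison and the sample size are not touched. The change is worth making because it replaces a figure open to misreading with one that answers the stated objective.

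**What to change.** In protocol section 10.3.7.6 and SAP section 7.9.4.6:

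- Estimate the cumulative incidence of resumption from infusion in the Roctavian Cohort, by Kaplan-Meier, or by Aalen-Johansen with death as a competing event.
- Censor at the end of the last registry data entry period, as section 8.2 already provides.
- Report estimates with 95% confidence intervals at 12, 24 and 36 months, as far as follow-up allows at each interim.
- Give participants who never ended prophylaxis as a separate count, so that they are not read as lasting successes.
- Keep the mean and median only if they are labelled as conditional on having resumed within follow-up.
- Align the two population statements, and add the estimates to table shell 18.

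The cost is one further table and a paragraph. The dates of gene therapy and of return to prophylaxis are already collected, so no new data are needed.

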10.3.8. Other Analyses

Per the resolution requiring the Routine Data Collection and Evaluations for Valoctocogene Roxaparvovec ([AM-RL 2023](#)), additional analyses comparing outcomes between the Roctavian Cohort and classes of SoC prophylaxis (eg, SHL FVIII, EHL FVIII, PD FVIII, and emicizumab), age groups, as well as for the SoC Cohort that is AAV 5 antibody negative will be evaluated. (Note that PwSHA treated with Roctavian will be AAV5 negative per the indication for use in Europe.)

The feasibility of conducting comparative analyses for subgroups will be described during the 18-month interim report, though analyses are planned *a priori*. As the therapeutic treatment strategy for an individual who consents to this study is made independently of the decision to participate in the study, the sample size of specific sub-cohorts by SoC therapeutic classes is not known. The feasibility of conducting a comparative analysis will be based on the characteristics of the sub-cohort, which will impact the ability of the PS to address confounding, as well as sample size. Similarly, the use of AAV antibody testing among PwSHA who are not considering gene therapy is not known currently. AAV antibody status is not known to impact clinical outcomes among PwHA and therefore is not part of routine clinical practice currently. The feasibility of a comparison to AAV 5 negative among those in the SoC Cohort will be evaluated similarly to the SoC therapeutic classes (based on both characteristics and sample size). Feasibility of analyses will also consider the ability to conduct comparisons for all vs specific objectives (eg, it may be possible to conduct subgroup analyses for the primary objective, but not for secondary objectives due to missing data). It is assumed *a priori* that analyses will be feasible.

In addition to the evaluation of the pre-specified sub-group analysis regarding SoC therapeutic classes and AAV 5 antibody status, other sub-group analyses may be considered based on the observed characteristics of the cohorts that consent into the AbD. As the characteristics of the PwSHA in Germany who will receive Roctavian are not known, nor the characteristics of those on SoC therapies who will consent into the AbD, any additional analyses will be detailed in the SAP and discussed in the interim reports (described below).

10.4. Interim Analyses

Interim reports are planned at 18, 36 and 54 months after initiation of this study.

Full interim analyses of all endpoints are planned at 18-, 36- and 54-month reports. The data reflected in these interim analyses are expected to reflect data captured in the DHR through approximately 4 to 6 months prior to the interim analysis as the interim analysis points reflect

submissions of interim reports. Study sites will be asked to update data for all AbD participants approximately 6 months prior to the planned interim analysis and will be supported by site monitors through on-site monitoring and routine monitoring visits to ensure that all available data for enrolled participants are recorded into the DHR prior to the planned interim analysis. These interim analyses in the 18-, 36- and 54-month reports will focus on the primary analyses but will not conduct the sensitivity analyses discussed in Section 10.3.8. The feasibility of sensitivity analyses, along with other sub-group analyses that are planned, will be discussed in these reports.

The SAP further describes the planned interim analyses in greater detail.

10.5. Limitations of the Research Methods

Due to the observational nature of this study, results will represent a range of real-world practice in Germany, though results may be influenced by site heterogeneity (eg, clinic structure, site specific clinical practices). The analysis intends to utilize site as a component of the propensity score (and will consider an analysis by site if necessary). Due to the regulations governing the DHR, data extracts from the DHR cannot (at the time of drafting this protocol) provide specific site identification numbers. Based on discussions with the DHR, it is anticipated that although site identification numbers cannot be provided, that participants managed at the same site will be able to be identified. If it is ultimately not possible to identify participants at the same site, the analysis will be limited in controlling for differential clinical management practices (eg, recommendations for specific FVIII prophylaxis regimens, use of FVIII for suspected bleeds that may be anthropic associated pain), as well as reporting/recording practices that may differ between sites.

As discussed in Section 10.3.8, the characteristics of the population that utilizes Roctavian in the real world is not currently known and similarly the SoC population that will consent to the AbD is also not known. It is expected that due to the resolution restricting authority to provide care to those providers who participate in the required data collection ([AM-RL 2023a](#)) the Roctavian Cohort will be generalizable to the full population administered Roctavian in Germany. The generalizability of the SoC Cohort and similarity of the cohort to the Roctavian Cohort may be impacted by selection bias. PS will be utilized to address differences between the cohorts, though the ability of the PS (along with additional adjustments/clustering if needed) to control for these differences cannot be assessed until after data collection begins. It is anticipated that the methods described in this protocol and accompanying SAP will control for potential confounding and allow for an unbiased comparison between the cohorts.

Although the methods described in this protocol and accompanying SAP are anticipated to be able to control for potential confounding (particularly for comparisons of clinical measures such as bleeds), it is anticipated that some potential variables that could impact clinical measures, such as bleeds, and clinical outcomes assessments will not be captured in the DHR. In particular, individual lifestyle choices (eg, participation in sports and physical

activities) and personal experience with hemophilia A (eg, individual discernment between a joint bleed vs joint pain, effectiveness of previous treatments) are not feasible to capture in an observational registry. The capture of these individualized components of disease experience would be difficult to capture even in an interventional clinical trial setting. While residual FVIII activity has been identified to account for around 70% of a bleeding phenotype, the remaining 30% is potentially related to other unexplained individual variables ([Mancuso 2018](#)). It is anticipated that this individualized participant experience is particularly relevant for patient centric measures, such as health related quality of life, joint function and pain. These measures would be most clinically meaningfully described based on intra-participant comparisons, which accounts for the individualized management of hemophilia symptoms, as well as previous experiences with an individual's disease that are not possible to capture in a registry. Although, intraindividual comparisons would better control for an individual's experience, the AbD requires comparisons across cohorts. Use of responder analyses, as well as the potential inclusion of target joints in the PS particularly for joint health, are anticipated to address some of potential confounding from variables that are not possible to collect in an observational registry. In addition to variables that are not feasible to capture in an observational registry, the non-interventional nature of the study reflecting a range of real-world practice in German could introduce confounding that cannot be fully addressed with PS or specific applications of the PS (eg, matching). For example, persons with severe hemophilia A are recommended to be treated with hemostatic prophylaxis, though a small portion of the severe hemophilia A population in Germany may still be utilizing an on-demand treatment regimen. Persons utilizing an on-demand regimen are likely to have a higher baseline bleeding rate, as prophylaxis is associated with reduce bleeding events. All persons administered commercially available Roctavian are expected to have received hemostatic prophylaxis treatment for at least 12 months by the time that a participant will be treated with Roctavian gene therapy. If persons treated with an on-demand regimen for part of the baseline period enroll into the SOC Cohort, these participants may have outlier propensity scores which may not be able to be matched. The proportion of on-demand participants in the SOC Cohort, as well as impact of these participants on the analysis will be discussed in interim and final reports.

For safety outcomes, PS may be less likely to control for potential confounding due to the expected rarity of the safety events of interests. The risk of spurious findings for the safety comparisons are particularly notable for 'all-cause' outcomes that do not consider relationship to hemophilia treatment as characteristics of the cohort. For example, if one cohort is older, events due to unrelated causes (ie, risks associated with older age) could be misinterpreted to be associated with a product.

The data utilized for this analysis will be collected in the DHR. The DHR has the advantage of being an existing system with which German physicians are familiar and should minimize site burden for additional data collection specific to the AbD, though the DHR is more similar to a secondary data source for the purposes of this analysis. Due to the anonymized nature of the DHR, the DHR will be treated as the source data for the purposes of source data

verification (see Section 11.8). Data fields in the DHR were reviewed in the design of this study and additional data fields were requested to be added as needed. Despite these considerations in the design of the study, the administration of the DHR is not controlled by the study sponsor and therefore the potential for missing data and/or implausible data values are possible. Data monitoring activities (described in Section 11.8) are anticipated to minimize missing data and implausible values in the final data set, though data for interim analyses may be more prone to potential missing/erroneous data. As missing/erroneous data are possible, the extent of missing data (or data excluded due to implausible values) will be quantified (when applicable). Imputation for missing data may be considered based on the patterns of missingness and effect of missing data on the interpretability of the results. Further detail regarding missing data procedures will be documented in the SAP.

